5.3.1 Adverse Event Reporting Period

Investigators will seek information on adverse events at each patient contact. All adverse events, whether reported by the patient or noted by study personnel, will be recorded in the patient's medical record and on the Adverse Event eCRF.

After informed consent has been obtained but prior to initiation of study drug, only serious adverse events caused by a protocol-mandated intervention (e.g., invasive procedures such as biopsies, discontinuation of medications) should be reported (see Section 5.4.2 for instructions for reporting serious adverse events).

After initiation of study drug, all adverse events will be reported until 8 weeks after the last dose of study drug the patient receives.

Instructions for reporting adverse events that occur after the adverse event reporting period are provided in Section 5.6.

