3.1.1 Internal Monitoring Committee and Scientific Oversight Committee

Regular safety reviews for this OLE will be performed by the Sponsor's IMC in combination with the Scientific Oversight Committee as outlined in the IMC-Scientific Oversight Committee Agreement. If necessary, cumulative unblinded data for patients remaining in the parent Study GA30044 may also be made available to IMC and Scientific Oversight Committee members. This committee will include a clinical scientist, in conjunction with a safety scientist, biostatistician, two external SLE experts who are not investigators in this study and statistical programmers from the Sponsor who are not members of the Study Management Team. The committee members will not have direct contact with investigational staff or site monitors. The committee may request that additional Sponsor scientists (e.g., clinical pharmacologist, biomarker) participate in data analysis. This committee will review safety data and make recommendations to the Sponsor regarding continuation of the study and/or study drug dose modifications. After each meeting, either IMC or the Scientific Oversight Committee will recommend that the Sponsor proceed with one of the four following actions: 1) continue the study unchanged, 2) discontinue the study for safety reasons, 3) discontinue the study for futility (based on analysis of the blinded Study GA30044), or 4) amend the study protocol. For further information, please see the IMC and Scientific Oversight Committee Agreement.

3.2 **END OF STUDY AND LENGTH OF STUDY**

The end of this study is defined as the date when the last patient, last visit occurs. The end of the study is expected to occur 56 weeks after the last patient is enrolled.

The maximum time in the study for a patient is 56 weeks, including treatment for 48 weeks and an 8-week safety follow-up period after the last dose of GDC-0853. The total length of the study, from enrollment of the first patient to the end of the study, is expected to be approximately 3.5 years.

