4.1.1 Inclusion Criteria

Patients must meet the following criteria for study entry:

- Signed Informed Consent Form (see Section 4.4.1)
- Age 18–76 years, inclusive, at time of signing Informed Consent Form
- Able to comply with the study protocol, in the investigator's judgment
- Completion of Study GA30044 up to 48 weeks
- Acceptable safety and tolerability during Study GA30044 as determined by the investigator
- Women of childbearing potential must have a negative urine pregnancy test at baseline

A serum pregnancy test is needed on Day 1 only if the urine pregnancy test is positive.

- For women of childbearing potential (including those who have had a tubal ligation): Agreement to remain abstinent (refrain from heterosexual intercourse) or use a contraceptive method with a failure rate of < 1% per year during the treatment period and for at least 60 days after the last dose of study drug.

A woman is considered to be of childbearing potential if she is postmenarcheal, has not reached a postmenopausal state (≥ 12 continuous months of amenorrhea with no identified cause other than menopause), and has not undergone surgical sterilization (removal of ovaries and/or uterus).

Examples of contraceptive methods with a failure rate of < 1% per year include bilateral tubal ligation, male sterilization, established proper use of hormonal contraceptives that inhibit ovulation, hormone-releasing intrauterine devices, and copper intrauterine devices. Women using estrogen-containing hormonal contraceptives as a method of contraception must also use a barrier, such as a male condom, in conjunction with the hormonal contraceptives.

The reliability of sexual abstinence should be evaluated in relation to the duration of the clinical trial and the preferred and usual lifestyle of the patient. Periodic abstinence (e.g., calendar, ovulation, symptothermal, or postovulation methods) and withdrawal are not acceptable methods of contraception.

- For men: agreement to remain abstinent (refrain from heterosexual intercourse) or use contraceptive measures, and agreement to refrain from donating sperm, as defined below (also see [Appendix 5](#))

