4.1.2 Exclusion Criteria

Patients who meet any of the following criteria will be excluded from study entry:

- Met protocol-defined treatment-stopping criteria during Study GA30044
- An adverse event in Study GA30044 that required permanent discontinuation of study drug
- During Study GA30044, treatment with any therapy that is prohibited in this study (see Section [4.3.2](#))
- In the opinion of the investigator, any new (since initially enrolling in the Phase II Study GA30044), significant, uncontrolled comorbidity or new clinical manifestation (related to SLE or not) that 1) requires medications not allowed in this protocol (see Section [4.3.2](#)) or 2) could put the patient at undue risk from a safety perspective

If the Principal Investigator has questions related to exclusion, he or she should consult the Medical Monitor.

- Pregnant or breastfeeding, or intending to become pregnant during the study or within 60 days after the last dose of study drug
- Any uncontrolled or clinically significant laboratory abnormality that would affect safety, interpretation of study data, or the patient's participation in the study in the opinion of the investigator in consultation with the Medical Monitor
- Any major episode of infection requiring hospitalization or treatment with IV antibiotics within the last 4 weeks of Study GA30044
- Evidence of active, latent, or inadequately treated infection with *Mycobacterium tuberculosis* (TB) as defined as follows:
 - A positive QuantiFERON[®]-TB Gold (QFT) or T-SPOT[®] TB test or a Mantoux purified protein derivative (PPD) skin test (performed per Centers for Disease

Control and Prevention [CDC] guidelines using 5 tuberculin units per 0.1 mL) result of ≥ 5 mm of induration, performed at the Week 44 visit of Study GA30044 or later, prior to entry into Study GA30066

- Patients with a history of bacillus Calmette-Guérin vaccination should be screened using the QFT test only.
- A positive QFT test should be considered a positive diagnostic TB test.
- If initial QFT is indeterminate, perform a confirmatory test with either QFT or T-SPOT. The Principal Investigator may consult with the Medical Monitor to discuss selection of confirmatory test based on the patient's disease status and baseline immunosuppression.
- An indeterminate QFT test followed by a negative QFT or negative T-SPOT test should be considered a negative diagnostic TB test.

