5.4.3 Reporting Requirements for Pregnancies

5.4.3.1 Pregnancies in Female Patients

Female patients of childbearing potential will be instructed to immediately inform the investigator if they become pregnant during the study or within 8 weeks after the last dose of study drug. A paper Clinical Trial Pregnancy Reporting Form should be completed and submitted to the Sponsor or its designee immediately (i.e., no more than

24 hours after learning of the pregnancy), either by faxing or by scanning and emailing the form using the fax number or email address provided to investigators. Pregnancy should not be recorded on the Adverse Event eCRF. The investigator should discontinue study drug and counsel the patient, discussing the risks of the pregnancy and the possible effects on the fetus. Monitoring of the patient should continue until conclusion of the pregnancy. Any serious adverse events associated with the pregnancy (e.g., an event in the fetus, an event in the mother during or after the pregnancy, or a congenital anomaly/birth defect in the child) should be reported on the Adverse Event eCRF. In addition, the investigator will submit a Clinical Trial Pregnancy Reporting Form when updated information on the course and outcome of the pregnancy becomes available.

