5.4.3.2 Pregnancies in Female Partners of Male Patients

Male patients will be instructed through the Informed Consent Form to immediately inform the investigator if their partner becomes pregnant during the study or within 120 days (4 months) after the last dose of study drug. A paper Clinical Trial Pregnancy Reporting Form should be completed and submitted to the Sponsor or its designee immediately (i.e., no more than 24 hours after learning of the pregnancy), either by faxing or by scanning and emailing the form using the fax number or email address provided to investigators. Attempts should be made to collect and report details of the course and outcome of any pregnancy in the partner of a male patient exposed to study drug. The pregnant partner will need to sign an Authorization for Use and Disclosure of Pregnancy Health Information to allow for follow-up on her pregnancy. After the authorization has been signed, the investigator will submit a Clinical Trial Pregnancy Reporting Form when updated information on the course and outcome of the pregnancy becomes available. An investigator who is contacted by the male patient or his pregnant partner may provide information on the risks of the pregnancy and the possible effects on the fetus, to support an informed decision in cooperation with the treating physician and/or obstetrician.

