- ^{dd} Patients will receive GDC-0853 BID starting on Day 1 and ending on the evening prior to the Week 48 visit of Study GA30066. GDC-0853 should be taken with water by mouth. The dates and times of the most recent prior meal and most recent prior dose of short-acting antacid, PPI, or H₂RA, last dose of oral study drug (prior to clinic visit), and timing of study drug administration in clinic should be recorded at clinic visits with PK and/or fasting lipid assessments.
- ^{ee} The last dose of blinded study drug in Study GA30044 is the p.m. dose on the evening before the Week 48 visit for all patients. For patients continuing into the OLE Study GA30066, the first open-label dose of GDC-0853 should be the a.m. dose on Week 48 (which is Day 1 of Study GA30066).

Appendix 2

Types and Doses of Standard Oral Treatments for Systemic Lupus Erythematosus Permitted in Study

Oral corticosteroids ^a	Equivalent dose (mg)
Hydrocortisone	20
Cortisone acetate	25
Prednisone	5
Prednisolone	5
Methylprednisolone	4
Dexamethasone	0.75
Betamethasone	0.75
Triamcinolone	4
Beclometasone	0.75
Deflazacort	6
Other ^c	—
Oral Immunosuppression and antimalarials ^b	
Azathioprine	1 to 2.5 mg/kg/day
Methotrexate	7.5 to 25 mg/week
Mycophenolate mofetil	500 to 2500 mg/day
Mycophenolic sodium	360 to 1800 mg/day
Hydroxychloroquine	200 to 400 mg/day
Chloroquine	100 to 250 mg/day
Quinacrine	100 to 200 mg/day
Other ^c	—

^a Cortisol (hydrocortisone) is the standard of comparison for glucocorticoid potency. Hydrocortisone is the name used for pharmaceutical preparations of cortisol.

^b Any combination of azathioprine, methotrexate, mycophenolate mofetil, or mycophenolic sodium is prohibited.

^c Other medications may apply based on region and should be consulted with the Medical Monitor.

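### The safety follow-up visit is fixed to study Day 393 ±7 instead of the actual last dose, so it can precede the end of the 8-week adverse event period; female pregnancy reporting (8 weeks) is also shorter than pregnancy avoidance (60 days).

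*Combined protocol and SAP*

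**What the plan says.** **Adverse events.** Section 5.3.1 requires that, once study drug has started, "all adverse events will be reported until 8 weeks after the last dose of study drug the patient receives". Section 5.4.2.2 sets the same limit for serious events and events of special interest. Section 3.2 describes the final part of the study as "an 8-week safety follow-up period after the last dose of GDC-0853". Sections 5.3.1 and 5.3.2 say how events are found: investigators ask, non-directively, whenever they see or speak to the patient.

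**Visits.** Appendix 1 puts Week 48 at Day 337 ±7 and the Week 56 safety follow-up at Day 393 ±7. Footnote dd has dosing "ending on the evening prior to the Week 48 visit of Study GA30066". No contact is scheduled between these two visits and none after the second.

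**Pregnancy.** Section 4.1.1 requires women of childbearing potential to use contraception or abstain "for at least 60 days after the last dose of study drug", and Appendix 5 repeats the 60 days. Section 4.1.2 excludes women "intending to become pregnant during the study or within 60 days after the last dose of study drug". Section 5.4.3.1 tells women to inform the investigator "if they become pregnant during the study or within 8 weeks after the last dose of study drug". For male patients, contraception (Section 4.1.1) and partner-pregnancy reporting (Section 5.4.3.2, "within 120 days (4 months) after the last dose of study drug") both run for 120 days.

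**The concern.** The reporting period is counted from the last dose, whereas the visit that should close it is counted from enrollment. The two agree on nominal dates. They come apart when the Week 48 visit, and with it the last dose, moves within its own window, or when the follow-up visit is held early.

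Long-term safety is the primary objective, and its endpoints include changes after as well as during administration. If the last planned contact comes before 56 days, events in the remaining days are found only if the patient volunteers them or comes in for another reason. The length of that unprompted tail would differ between patients for scheduling reasons alone.

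The pregnancy passages raise a related problem. A woman can conceive while the protocol still requires her to avoid pregnancy, yet after the instruction to report it has lapsed.

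**Working it through.** **Inputs**
- Week 48 visit: Day 337 ±7, so Day 330 to 344 (Appendix 1).
- Last dose: the evening before, so nominally Day 336, range Day 329 to 343 (Appendix 1, footnote dd).
- Safety follow-up visit: Day 393 ±7, so Day 386 to 400 (Appendix 1).
- Adverse event reporting: 8 × 7 = 56 days after the last dose (Section 5.3.1).
- Female pregnancy avoidance: at least 60 days (Sections 4.1.1 and 4.1.2, Appendix 5).

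**The plan's own figure.** Visit day = 7 × week + 1. Week 48 gives 7 × 48 + 1 = 337 and Week 56 gives 7 × 56 + 1 = 393, both as printed. The nominal interval is 393 − 336 = 57 days, within a day of the stated 8 weeks.

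**Interval from last dose to follow-up visit** (follow-up day minus last-dose day)

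| Case | Calculation | Days after last dose | Short of 56 |
|---|---|---|---|
| Both visits nominal | 393 − 336 | 57 | 0 |
| Week 48 on time, follow-up 7 days early | 386 − 336 | 50 | 6 |
| Week 48 on time, follow-up 7 days late | 400 − 336 | 64 | 0 |
| Week 48 7 days late, follow-up 7 days early | 386 − 343 | 43 | 13 |
| Week 48 7 days early, follow-up 7 days late | 400 − 329 | 71 | 0 |

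Of the 15 × 15 = 225 permitted pairs of visit days, 91 put the follow-up visit before 56 days and 147 put it before 60. These are counts of combinations, not probabilities; the documents say nothing about how visits will spread within their windows.

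**Alternative reading.** If the visit is taken as last dose + 56 ±7, it falls 49 to 63 days after the last dose, so it can still come up to 56 − 49 = 7 days early.

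**Early stoppers.** Sections 4.2.2.3.4 and 4.5.2 call it the 8-week visit, but Appendix 1 gives only Day 393. For illustration, a last dose on Day 169 (Week 24) puts 8 weeks at 169 + 56 = Day 225, not Day 393.

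**Pregnancy reporting.** The difference is 60 − 56 = 4 days. Section 5.4.3.1 also covers the time in the study. If a woman is taken to be in the study until her follow-up visit, the shortfall is 60 minus the later of 56 and the day of that visit:
- visit at 56 days or earlier: 4 days;
- nominal visit at 57 days: 60 − 57 = 3 days;
- visit at 60 days or later: none.

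**The case against.** The strongest reply is that nothing goes unreported by rule. The duty to report runs to 56 days whatever the visit date, and each event must be followed to resolution or stability (Section 5.5.1). A reader might infer that a compliant site could close follow-up at 43 days. The documents do not support that; only the planned occasion for asking is lost.

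Other parts of the reply also stand. The 43-day figure needs opposite extremes of two windows in the same patient, and the nominal visit does cover 56 days. Symmetric ±7-day windows are ordinary. Unscheduled visits collect adverse events, and patients are told to seek care for infection, bleeding and cytopenia. The text describes follow-up as 8 weeks after the last dose, but that reading still allows a visit at 49 days. Section 5.6 catches later events only if they are serious and believed related.

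Three further inferences go too far:
- **That post-treatment event counts are known to be low.** The documents give no event rate for this period, and the study is single-arm, so no treatment comparison is biased.
- **That every woman has a 4-day reporting gap.** Reporting during the study closes the gap for those seen at 60 days or later. Section 5.4.3.3 also makes congenital anomalies and abortions reportable without a stated time limit.
- **That the rabbit malformation exposure (10.6 µM·hr or more, Section 1.3.1) lies within the anticipated ceiling of 36 µM·hr (Section 3.3.1) and so shows risk on days 57 to 60.** The ceiling is a mean AUC during dosing. The readable text gives no half-life value or residual exposure that far off drug.

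**Conclusion.** The point holds as a gap in scheduled ascertainment and an inconsistency between passages. It does not show that events will be missed.

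The last planned contact can precede the end of the adverse event period by 6 days with an on-time Week 48 visit, and by 13 days (13/56 = 23%) in the extreme case. This rests on taking the Appendix 1 study days and windows as printed and the last dose as the evening before Week 48. How many patients would be affected, and how many events, cannot be estimated from the documents.

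The pregnancy reporting period is up to 4 days shorter than the avoidance period for women whose follow-up visit falls before 60 days. The passages must be reconciled; the documents do not settle whether 8 weeks or 60 days was intended. The shortfalls are short, but the study's primary objective is safety and the correction is cheap, so the change should be made.

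**What to change.** 1. In Appendix 1, count the safety follow-up visit from the actual last dose, for completers and early stoppers alike. Use a one-sided window that opens no earlier than the end of the reporting period, for example 56 days, -0/+7, which places the visit 56 to 63 days after the last dose.
2. Reconcile the 8-week wording in Section 5.4.3.1 with the 60 days in Sections 4.1.1 and 4.1.2 and Appendix 5, so that female pregnancy reporting is no shorter than pregnancy avoidance, as is already so for men. A visit at 56 to 59 days would still put the last scheduled pregnancy test before 60 days, so settle this period before fixing the window.

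**Cost.** No extra visit is needed. The last visit moves later for some patients: in the 43-day case by 56 − 43 = 13 to 63 − 43 = 20 days, about two to three weeks. With the latest permitted last dose (Day 343), the visit would fall on Day 399 to 406, beyond Week 56 (Day 393). The 56-week maximum and the end-of-study wording in the synopsis and Section 3.2 therefore need adjusting.

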5.3.2 Eliciting Adverse Event Information

A consistent methodology of non-directive questioning should be adopted for eliciting adverse event information at all patient evaluation timepoints. Examples of non-directive questions include the following:

"How have you felt since your last clinic visit?"

"Have you had any new or changed health problems since you were last here?"

5.3.3 Assessment of Severity of Adverse Events

The adverse event severity grading scale for the NCI CTCAE (v4.0) will be used for assessing adverse event severity. Table 4 will be used for assessing severity for adverse events that are not specifically listed in the NCI CTCAE.

Table 4 Adverse Event Severity Grading Scale for Events Not Specifically Listed in NCI CTCAE

Grade	Severity
1	Mild; asymptomatic or mild symptoms; clinical or diagnostic observations only; or intervention not indicated
2	Moderate; minimal, local, or non-invasive intervention indicated; or limiting age-appropriate instrumental activities of daily living ^a
3	Severe or medically significant, but not immediately life-threatening; hospitalization or prolongation of hospitalization indicated; disabling; or limiting self-care activities of daily living ^{b, c}
4	Life-threatening consequences or urgent intervention indicated ^d
5	Death related to adverse event ^d

NCI CTCAE = National Cancer Institute Common Terminology Criteria for Adverse Events.

Note: Based on the most recent version of NCI CTCAE (v4.0), which can be found at: http://ctep.cancer.gov/protocolDevelopment/electronic_applications/ctc.htm

^a Instrumental activities of daily living refer to preparing meals, shopping for groceries or clothes, using the telephone, managing money, etc.

^b Examples of self-care activities of daily living include bathing, dressing and undressing, feeding oneself, using the toilet, and taking medications, as performed by patients who are not bedridden.

^c If an event is assessed as a "significant medical event," it must be reported as a serious adverse event (see Section 5.4.2 for reporting instructions), per the definition of serious adverse event in Section 5.2.2.

^d Grade 4 and 5 events must be reported as serious adverse events (see Section 5.4.2 for reporting instructions), per the definition of serious adverse event in Section 5.2.2.

5.3.4 Assessment of Causality of Adverse Events

Investigators should use their knowledge of the patient, the circumstances surrounding the event, and an evaluation of any potential alternative causes to determine whether an adverse event is considered to be related to the study drug, indicating "yes" or "no" accordingly. The following guidance should be taken into consideration (see also [Table 5](#)):

- Temporal relationship of event onset to the initiation of study drug
- Course of the event, with special consideration of the effects of dose reduction, discontinuation of study drug, or reintroduction of study drug (as applicable)
- Known association of the event with the study drug or with similar treatments
- Known association of the event with the disease under study
- Presence of risk factors in the patient or use of concomitant medications known to increase the occurrence of the event
- Presence of non-treatment-related factors that are known to be associated with the occurrence of the event

Table 5 Causal Attribution Guidance

Is the adverse event suspected to be caused by the study drug on the basis of facts, evidence, science-based rationales, and clinical judgment?	
YES	There is a plausible temporal relationship between the onset of the adverse event and administration of the study drug, and the adverse event cannot be readily explained by the patient's clinical state, intercurrent illness, or concomitant therapies; and/or the adverse event follows a known pattern of response to the study drug; and/or the adverse event abates or resolves upon discontinuation of the study drug or dose reduction and, if applicable, reappears upon re-challenge.
NO	An adverse event will be considered related, unless it fulfills the criteria specified below. Evidence exists that the adverse event has an etiology other than the study drug (e.g., preexisting medical condition, underlying disease, intercurrent illness, or concomitant medication); and/or the adverse event has no plausible temporal relationship to administration of the study drug (e.g., cancer diagnosed 2 days after first dose of study drug).

For patients receiving combination therapy, causality will be assessed individually for each protocol-mandated therapy.

